Study size:	
Approximately 11700 patients; There are roughly 8500 AIS patients ≥ 18 years of age who have been treated with IV rtPA and 3200 patients who admitted to hospital within 4.5 hours of onset and did not receive reperfusion treatment from Jan 2017 to Mar 2020.
 
In the China National Stroke Registry I (2007-2008) the 12-month mortality rate for post-stroke patients is around 14%. For this study, it is assumed that 1-year mortality is 12% and 15% for the rt-PA treatment group and the group who did not receive reperfusion. In total, 6069 patients with treatment ratio 2:1 are needed to observe 855 events and to detect the difference (HR=0.79) with 2-sided alpha of 0.05 and 90% power. In addition, considering a treatment ratio 1:1 with the same assumption described above with power of 90% at a 2-sided, 5% significant level, roughly 5400 patients are needed to observe 756 events to detect the difference.
		

BOEHRINGER INGELHEIM Group of Companies

Non-interventional Study Protocol BI Study Number 0135-0350

Page 11 of 41
c36821715-01

Proprietary confidential information © 2021 Boehringer Ingelheim International GmbH or one or more of its affiliated companies

Name of company: Boehringer Ingelheim			
Name of finished medicinal product: Actilyse			
Name of active ingredient: Alteplase			
Protocol date: 2 Sep 2021	Study number: 0135-0350	Version/Revision: 1.0	Version/Revision date: NA

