9. RESEARCH METHODS

A) STUDY DESIGN

[figure not shown]
This study is a non-interventional study (NIS) based on existing data. We will analyse data of AIS patients aged ≥ 18 years in China collected from the ZSQCC platform. [\[P21-04780\]](#), [\[P21-04783\]](#), [\[P21-04784\]](#), [\[P21-04779\]](#), [\[P21-04782\]](#)

Patients meeting the inclusion and exclusion criteria will be divided into 2 cohorts:

- IV rt-PA cohort: Patients who received IV rt-PA within 4.5 hours of symptom onset
- Non-reperfusion cohort: Patients who arrived or were admitted to the hospital within 4.5 hours of symptom onset and did not receive any reperfusion treatment

The flow of data selection for each of the 2 reporting patient cohorts is depicted in [Figure 1](#) below.

Figure 1 Patient cohorts selected for the non-interventional study

Note: dotted lines: excluded

B) SETTING

i. Study sites

In this study, AIS patient data from 80 stroke centres in the ZSQCC platform from January 2017 to March 2020 will be used.

ii. Study population

No sampling will be undertaken and all patients who meet all the inclusion criteria and none of the exclusion criteria will be included.

The inclusion and exclusion criteria are listed below:

Inclusion criteria:

- Patients registered in the ZSQCC platform from Jan 2017 to Mar 2020
- ≥ 18 years of age
- Diagnosed with AIS at admission
- Arrived or admitted to the hospital within 4.5 hours of symptom onset
- If treated with IV rt-PA: received IV rt-PA within 4.5 hours of symptom onset

Exclusion criteria:

- Documented IVT contraindication except age to IV rt-PA treatment according to the SmPC
- Missing any one of the key data (age, gender, baseline National Institutes of Health Stroke Scale [NIHSS], time of symptom onset, time of hospital arrival or admission, IVT or not, time of IV rt-PA treatment)
- Received thrombolysis agents other than rt-PA (urokinase, tenecteplase, recombinant plasminogen activator, prourokinase, streptokinase)
- Received endovascular treatment
- Received IV rt-PA after 4.5 hours of symptom onset

iii. Study visits

Not applicable.

iv. Study discontinuation

Boehringer Ingelheim (BI) reserves the right to discontinue the study at any time for the following reason:

- Violation of Good Pharmacoprevention Practice (GPP), the study protocol, or the contract by study site, investigator or research collaborator, disturbing the appropriate conduct of the study

C) VARIABLES**i. Exposures**

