The database includes patient demographic information, baseline clinical characteristics, indicators related to diagnosis and treatment during hospitalisation and follow-up after discharge. The platform staffs tried to follow up all discharged patients by a phone call at 1-year discharge. Telephone follow-up of the platform was conducted by platform staffs. The follow-up standards were unified, and telephone recordings were all kept. Neurologists conducted trainings at regular intervals for platform staffs and randomly checked the telephone recordings. Several studies based on this dataset were approved by the Second Affiliated Hospital of Zhejiang University Institutional Review Board (IRB) and were published in peer-reviewed journals. [\[P21-04780\]](#), [\[P21-04783\]](#), [\[P21-04784\]](#), [\[P21-04779\]](#), [\[P21-04782\]](#)

E) STUDY SIZE

There were approximately 8500 AIS patients (≥ 18 years of age) who were treated with IV rt-PA and 3200 patients who were admitted to the hospital within 4.5 hours of symptom onset and did not receive reperfusion treatment from Jan 2017 to Mar 2020.

In the China National Stroke Registry I (2007-2008), the 12-month mortality rate for post-stroke patients was approximately 14%. [\[R21-1852\]](#) For this study, it is assumed that 1-year mortality is 12% and 15% for the rt-PA treatment cohort and the cohort who did not receive reperfusion, respectively. In total, 6069 patients with a treatment ratio 2:1 are needed to observe 855 events and to detect the difference (hazard ratio=0.79) with a 2-sided alpha of 0.05 and 90% power. In addition, considering a treatment ratio 1:1 with the same assumption described above with power of 90% at a 2-sided, 5% significant level, roughly 5400 patients are needed to observe 756 events to detect the difference.

F) DATA MANAGEMENT

The data will be managed by ZSQCC. The source codes for data management and data analyses will be kept for inspection for at least 5 years after publication of the results.

Full details of the data management plan are documented in a separate NIS-Data Management and Review Plan (NIS-DMRP).

G) DATA ANALYSIS

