7. RESEARCH METHODS

7.1 STUDY DESIGN

This study is a non-interventional study (NIS) based on existing data. We will analyse data of AIS patients aged ≥ 18 years in China collected from the ZSQCC platform. [\[P21-04780\]](#), [\[P21-04783\]](#), [\[P21-04784\]](#), [\[P21-04779\]](#), [\[P21-04782\]](#)

Approximately 11700 AIS patients in total are recorded in the ZSQCC platform and will be analysed in this study. There were approximately 8500 AIS patients (≥ 18 years of age) who were treated with IV rt PA and 3200 patients who were admitted to the hospital within 4.5 hours of symptom onset and did not receive reperfusion treatment from Jan 2017 to Mar 2020. In the China National Stroke Registry I (2007-2008), the 12-month mortality rate for post-stroke patients was approximately 14%. [\[R21-1852\]](#) For this study, it is assumed that 1-year mortality is 12% and 15% for the rt-PA treatment cohort and the cohort who did not receive reperfusion, respectively. In total, 6069 patients with a treatment ratio 2:1 are needed to observe 855 events and to detect the difference (hazard ratio=0.79) with a 2-sided alpha of 0.05 and 90% power. In addition, considering a treatment ratio 1:1 with the same assumption described above with power of 90% at a 2-sided, 5% significant level, roughly 5400 patients are needed to observe 756 events to detect the difference.

[figure not shown]
Patients meeting the inclusion and exclusion criteria will be divided into 2 cohorts:

- IV rt-PA cohort: Patients who received IV rt-PA within 4.5 hours of symptom onset
- Non-reperfusion cohort: Patients who arrived or were admitted to the hospital within 4.5 hours of symptom onset and did not receive any reperfusion treatment

Propensity score matching (PSM) will be used to match the baseline characteristics between the above 2 cohorts. The primary, secondary outcomes, as well as baseline characteristics will be compared between the matched cohorts.

The flow of data selection for each of the 2 reporting patient cohorts is depicted in Figure 1 below.

Figure 1 Patient cohorts selected for the non-interventional study

Note: dotted lines: excluded

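### Protocol 9.E: at the assumed 12%/15% mortality, 6069 patients (2:1) give 789 events, not 855, and 5400 (1:1) give 729, not 756; the effect on power is minor

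*Protocol*

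**What the plan says.** Protocol 9.E (Study size) sets out the following in one paragraph.

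- Background: in a national stroke registry, "the 12-month mortality rate for post-stroke patients was approximately 14" per cent.
- Planning rates: "it is assumed that 1-year mortality is 12% and 15% for the rt-PA treatment cohort" and the non-reperfusion cohort, in that order.
- 2:1 design: "In total, 6069 patients with a treatment ratio 2:1 are needed to observe 855 events and to detect the difference (hazard ratio=0.79", at two-sided alpha 0.05 and 90% power.
- 1:1 design, on the same assumptions: "roughly 5400 patients are needed to observe 756 events to detect the difference".
- Available data: about 8500 rt-PA patients and "3200 patients who were admitted to the hospital within 4.5 hours of symptom onset and did not receive reperfusion treatment".

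The Protocol abstract ("In total, 6069 patients with treatment ratio 2:1 are needed to observe 855 events and to detect the difference (HR=0.79") and SAP 7.1 ("In total, 6069 patients with a treatment ratio 2:1 are needed to observe 855 events") carry the same figures. Neither document says which cohort is the 2 in 2:1. No dropout allowance or other parameter is given.

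The sizes do not limit inclusion. Protocol 9.B says: "No sampling will be undertaken and all patients who meet all the inclusion criteria and none of the exclusion criteria will be included". They are used once more, as the minimum subgroup size in the Protocol abstract and 9.G. SAP 11.1 lists the same subgroups without a minimum.

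**The concern.** Mortality, patient numbers and event counts are stated together, and any two of them fix the third. Here they do not agree. The stated pairs imply overall mortality of 855/6069 = 14.1% and 756/5400 = 14.0%, whereas 12% and 15% average 13.0% at 2:1 and 13.5% at 1:1.

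Events drive the power of the planned log-rank and Cox analyses, so this is the figure a second analyst would try to reproduce. If the mortality assumption held exactly, a matched set of 6069 would show about 789 deaths and would appear to have missed its target.

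A separate inconsistency affects how the power statement is read. Protocol 9.G says that no formal hypothesis tests or cohort comparisons are planned. Section 8 sets a comparison as the primary objective, 9.E gives alpha and power, and SAP 11.1 plans chi-square and log-rank tests and Cox models.

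**Working it through.** **Inputs (Protocol 9.E).** Mortality 0.12 (rt-PA) and 0.15 (non-reperfusion); HR 0.79; two-sided alpha 0.05; power 90%; N = 6069 (2:1) and 5400 (1:1). I take 2:1 as two rt-PA patients per non-reperfusion patient, because about 8500 and 3200 are available. (1.960 + 1.282)² = 10.507. f is the rt-PA fraction.

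**1. Each stated figure taken alone.**
- Schoenfeld events, d = 10.507 / [f(1−f)(ln HR)²], at HR 0.79: 851 at f = 2/3 (stated 855) and 756.4 at f = 1/2 (stated 756).
- Two-proportion sample size for 15% v 12%: 2030 × 3 = 6090 (stated 6069) and 2725 × 2 = 5450 (stated 5400).

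All four stated figures are within 1%. The problem lies in the pairing.

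**2. Events from the stated sizes.**
- 2:1: 4046 × 0.12 + 2023 × 0.15 = 485.5 + 303.5 = 789, which is 66 (7.7%) below 855.
- 1:1: 2700 × 0.12 + 2700 × 0.15 = 324 + 405 = 729, which is 27 (3.6%) below 756.

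**3. The hazard ratio that the rates imply.** Under proportional hazards, HR = ln(0.88)/ln(0.85) = 0.7866, which rounds to 0.79.
- 1:1: d = 729.3, and 729.3/0.135 = 5402 patients. The stated 5400 is therefore right for these rates.
- 2:1: d = 820.4, and 820.4/0.130 = 6311, or 6312 to divide by three (4208 + 2104).

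**4. Power at the stated sizes.** Log-rank power = Φ(√[d f(1−f)] × |ln HR| − 1.960).

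| Design | Events | HR 0.787 | HR 0.79 | Two-proportion test |
|---|---|---|---|---|
| 6069 (2:1) | 789 | 88.9% | 87.7% | 89.9% |
| 5400 (1:1) | 729 | 90.0% | 88.9% | 89.7% |

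**5. Can one reading rescue both pairs?**
- Rounding the HR to 0.79 explains 756 at 1:1. At 2:1 it explains roughly 855 events, but not 6069 patients alongside them.
- A 14% overall rate gives 5400 × 0.14 = 756 exactly and 6069 × 0.14 = 850, but it is not the stated planning assumption.
- Reversed allocation gives 2023 × 0.12 + 4046 × 0.15 = 850, but needs 4046 controls when about 3200 exist, and it leaves the 1:1 pair unexplained.
- Freedman's formula, one-sided alpha, HR 0.80, a continuity correction and 13 months of follow-up also fail to reconcile both pairs with 12%/15%.

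**The case against.** The strongest reply is that the patient numbers are sound and nothing depends on the event counts. Much of that stands. At 1:1 the size is correct for the plan's own rates, and 756 is simply what the rounded hazard ratio requires. At 2:1 the shortfall is about one point of power at the implied hazard ratio and almost nothing by a two-proportion test. The data already exist and every eligible patient is included, so no recruitment decision changes. What the reply does not remove is that the event counts in three places do not follow from the stated rates, and that rounding the hazard ratio does not explain the 2:1 pair.

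A reader might go further in three ways that the documents do not support.

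- **The registry's 14% was substituted for the planning rates.** The 1:1 pair fits that exactly, but it equally fits the rounded hazard ratio. The documents do not settle which was used.
- **Both sizes are too small for 90% power.** Converting events at the rounded 0.79 into patients at 12%/15% gives larger sizes, but those rates imply 0.787. That conversion mixes inputs again and would raise a 1:1 size that is already right.
- **A matched set of 6069 would trip the rule that at least half the rt-PA cohort be matchable.** 4046/8500 is 47.6%, but 6069 is a minimum size, not the expected matched set. The 8500 is approximate and is not said to be net of all exclusions; with 8092 or fewer eligible rt-PA patients, 4046 would meet 50%.

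**Conclusion.** The point holds as a minor arithmetic inconsistency. The event counts are overstated by 66 at 2:1 and 27 at 1:1 relative to the plan's own mortality. At 1:1 only the event count is wrong, since 5400 patients give 90.0% log-rank power at the implied hazard ratio. At 2:1, 6069 patients give 88.9% (87.7% at the rounded 0.79), a little below the stated 90%. This is not evidence that the study is underpowered.

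These figures assume that 2:1 means two rt-PA patients per control, proportional hazards, one year of complete follow-up, and the usual formulas for independent groups. The cause of the mismatch is not stated.

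The contradiction between the Protocol 9.G sentence and the objective, power statement and SAP 11.1 is real, but does not depend on this arithmetic.

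**What to change.** In the Protocol abstract, Protocol 9.E and SAP 7.1, state that 2:1 means two rt-PA patients per non-reperfusion patient, that 12%/15% convert events to patients, and that the hazard ratio is 0.787 before rounding. Then choose one:

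- **Keep the sizes.** 6069 patients, 789 events, about 89% log-rank power (2:1); 5400 patients, 729 events, 90% power (1:1).
- **Keep 90% power at HR 0.787.** About 821 events from 6312 patients (2:1), and about 730 events from 5402 patients (1:1).

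If a size changes, carry it into the subgroup minimum in the Protocol abstract and 9.G.

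Separately, remove or reword the 9.G sentence on no formal testing or comparisons, and check that the nearby statement calling the analyses generally descriptive, and the Annex 2 entries on hypotheses and measures of association, agree with the result.

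The cost is wording and figures only; no data or analyses are added. The first option lowers the stated 2:1 power by about one point. The second raises the stated sizes by 243 and 2, within the approximate 8500 and 3200 available before exclusions, matching and follow-up losses.

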Data analysis: To account for potential confounding, the study cohorts (patients who received IV rt-PA and patients who did not receive reperfusion treatment) will be matched using the propensity score matching (PSM) method. Propensity score will be derived from predicted probabilities of treatment initiation. The PSM aims to balance the 2 treatment cohorts on baseline covariates. The feasibility of PSM will be evaluated based on available sample size and descriptive results. If patient characteristic between the two groups are significantly different, i.e., less than 50% of patients in the iv. rt-PA group can be matched to the non-reperfusion group based on PSM, then the study design will be re-evaluated before proceeding to analysis. The Nearest Neighbour method of PSM will be used to select the matched samples. All the variables listed in the covariates will be considered. Covariates including duration of hospitalization and reasons for untreated with rt-PA are only for descriptive analysis. The distribution of baseline characteristics will be presented before and after the matching process. For baseline covariates that are not sufficiently balanced after PSM, the covariates will be included in an appropriate multivariate model to adjust for those differences. Main analysis: Baseline characteristics of patients who received IV rt-PA and who didn't receive reperfusion treatments will be described, both before and after PSM. Absolute standardised difference (ASD) between the propensity score (PS)-matched cohorts will be calculated, in which a $\geq 10\%$ ASD will be considered a meaningful difference. In the primary analysis, all patients who received endovascular treatment will be excluded. For the primary outcome, all-cause mortality at 1-year (mRS=6), will be evaluated using Kaplan-Meier curve. The percentage of 1-year mortality with 95% confidence intervals (CIs) in the 2 PS-matched cohorts will be calculated separately. Cox regression models will be used to estimate the hazard ratio for the primary outcome between PS-matched cohorts. For the secondary outcomes, descriptive summaries will be conducted in the PS-matched cohorts separately. For categorical variables including functional independence (mRS 0-2), favourable clinical outcome (mRS 0-1) and outcome of mRS 5-6, the percentage and 95% CI will be calculated. A logistic regression model will be used to calculate odds ratios. For the			

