For the purpose of this study, analyses will generally be descriptive in nature and will be conducted using SAS statistical software (version 9.3 or higher). Descriptive data regarding patient demographic and clinical characteristics will be calculated. For categorical measures, data will include the frequency (number of cases [n]) and percentage (%) of total study patients observed in each category (N). All variables will be summarised descriptively through tabular displays of mean, median, ranges and standard deviations of continuous variables and frequency distributions of categorical variables. When necessary, continuous

variables also will be categorised into intervals, with the distribution of patients (n, N, %) for each interval provided.

The statistical analysis plan for the study is summarised below. Full details of the statistical analysis will be documented in the statistical and epidemiological analysis plan, which will be finalised before the end of data extraction.

As this is a NIS based on existing data, no formal hypothesis testing or comparisons between treatment cohorts are planned.

i. Main analysis

To account for potential confounding, the study cohorts (patients who received IV rt-PA and patients who did not receive reperfusion treatment) will be 1:1 or 2:1 matched by baseline characteristics using the propensity score matching (PSM) method. Propensity score (PS) will be derived from predicted probabilities of treatment initiation. The PSM aims to balance the 2 treatment cohorts on baseline covariates. The feasibility of PSM will be evaluated based on available sample size and descriptive results. If patient characteristics between the 2 cohorts are significantly different, i.e., less than 50% of patients in the IV rt-PA cohort can be matched to the non-reperfusion cohort based on PSM, the study design will be re-evaluated before proceeding to analysis. The Nearest Neighbour method of PSM will be used to select the matched samples. All the variables listed in the covariates will be considered. Covariates including duration of hospitalization and reasons for untreated with rt-PA are only for descriptive analysis. The distribution of baseline characteristics will be presented before and after the matching process. For baseline covariates that are not sufficiently balanced after PSM, the covariates will be included in an appropriate multivariate model to adjust for those differences.

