10. DATA MANAGEMENT AND SOFTWARE/TOOLS**10.1 SOFTWARE/TOOLS**

Propensity score matching (PSM) will be performed using R 4.0.5 (package: MatchIt) and other analyses will be conducted with SAS 9.4.

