To account for potential confounding, the 2 cohorts will be 1:1 or 2:1 matched by baseline characteristics using the Propensity Score Matching method. The feasibility of PSM will be evaluated based on available sample size and descriptive results. If patient characteristics between the 2 cohorts are significantly different, i.e., less than 50% of patients in the IV rt PA cohort can be matched to the non-reperfusion cohort based on PSM, the study design will be re-evaluated before proceeding to analysis. The PSM aims to balance the 2 cohorts on baseline covariates. The propensity score model will include age, gender, baseline NIHSS/NIHSS categories (0-4, 5-10, 11-15, 16-21, and ≥ 22), pre-stroke mRS, medical insurance status, smoking status, hospital level, diabetes, coronary artery disease, atrial fibrillation, prior stroke/transient ischaemic attack, hypertension, anti-platelet, lipid lowering, oral anticoagulation, and time from symptom onset to hospital admission. The method of Nearest Neighbour matching will be used (a maximum caliper width equal to 0.2 of the standard deviation of the logit of the propensity score) to select the matched samples. Then we will compare the baseline characteristics of the 2 propensity-score-matched cohorts. The absolute standardized difference (ASD) between the 2 PS-matched cohorts will be calculated, where at least 0.1 ASD will be considered a significant difference. For baseline covariates that are not sufficiently balanced after PSM, they will be included in an appropriate multivariate model to adjust for those differences.

For the primary outcome, a comparison of the percentage of 1-year* all-cause mortality (mRS=6) between the 2 matched cohorts will be conducted using a Chi-square test. A Kaplan-Meier curve with log-rank test will be used to analyse the data. Cox regression models will be used to estimate hazard ratios (95% confidence interval) between the 2 matched cohorts.

For the secondary outcomes, descriptive summaries will be conducted in the PS-matched cohorts separately. For the categorical variables including functional independence (mRS 0-2), favourable clinical outcome (mRS 0-1), and mRS 5-6 at 1 year, the Chi-square test and conditional logistic regression model will be conducted. For the distribution of mRS score at 1 year, the Wilcoxon rank sum test and ordinal logistic regression model will be performed to calculate the odds ratio and 95% CI.

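### The 50% matching-feasibility rule is taken over the larger cohort: with distinct 1:1 pairs it cannot be met on the stated counts (ceiling 37.6%), and the planned sample falls below it at both ratios

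*Protocol*

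**What the plan says.** Protocol 9.G.i says that the two cohorts "will be 1:1 or 2:1 matched by baseline characteristics using the propensity score matching (PSM) method". It then introduces a feasibility rule with the words "If patient characteristics between the 2 cohorts are significantly different" and explains that condition, by an i.e., as the case where "less than 50% of patients in the IV rt-PA cohort can be matched to the non-reperfusion cohort based on PSM". If so, the design is to be re-evaluated before the analysis goes ahead. The protocol abstract has the same rule ("less than 50% of patients in the iv. rt-PA group can be matched to the non-reperfusion group based on PSM"), and so does SAP 11.1 ("less than 50% of patients in the IV rt PA cohort can be matched to the non-reperfusion cohort based on PSM"). None of the three places ties the 50% to a matching ratio.

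Protocol 9.E and SAP 7.1 give about 8500 rt-PA patients and about 3200 non-reperfusion patients. They state a need for roughly 5400 patients (756 events) at 1:1, or 6069 patients (855 events) at 2:1. SAP 7.1 adds that approximately 11700 patients, which is 8500 + 3200, will be analysed.

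On the mechanics, SAP 11.1 specifies nearest-neighbour matching with "a maximum caliper width equal to 0.2 of the standard deviation of the logit of the propensity score", and SAP 10.1 says "Propensity score matching (PSM) will be performed using R 4.0.5 (package: MatchIt". Neither document says whether a non-reperfusion patient may be used more than once, or whether a patient who can be matched is one selected into a pair or one for whom a partner merely exists.

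**The concern.** The rule is worded as a test of whether the cohorts differ too much in their characteristics to be matched. A share of the larger cohort also depends on how many partners the smaller cohort can supply. With 2.66 rt-PA patients for every non-reperfusion patient (8500/3200), that supply can decide the result by itself.

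The rule would then give the same answer for perfect and for poor overlap. After a sound match of the planned size, the team would have either to re-evaluate the design or to set aside its own pre-specified rule. In a study of existing data, that leaves an important design choice open to discretion at the point where pre-specification should settle it.

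**Working it through.** **Inputs.** rt-PA cohort T = 8500 and non-reperfusion cohort C = 3200 (Protocol 9.E, SAP 7.1; both approximate). Threshold 50% of T (Protocol 9.G.i, SAP 11.1). Required sizes 5400 at 1:1 and 6069 at 2:1, hazard ratio 0.79, two-sided alpha 0.05, power 90% (Protocol 9.E).

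**Assumptions.** Matched sets are distinct, so no control is reused. The 2:1 ratio means two rt-PA patients per non-reperfusion patient.

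**1. The plan's own sizes reproduce.** Schoenfeld events = (1.960 + 1.282)² / [p(1−p)(ln 0.79)²].
- 1:1 (p = 1/2): 757 (stated 756).
- 2:1 (p = 2/3): 851 (stated 855).
- Patients at 1:1: 756/0.14 = 5400.
- A two-proportion calculation for 15% against 12% gives 5450 at 1:1 and 6090 at 2:1.

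All are within 3% of the stated figures, so the required sizes are taken as they stand.

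**2. Patients needed to pass.** 0.50 × 8500 = 4250 matched rt-PA patients. At 1:1 that takes 4250 distinct controls, and 4250 − 3200 = 1050 are lacking. At 2:1 it takes 4250/2 = 2125 controls with two partners each, which is 2125/3200 = 66.4% of the controls and 4250 + 2125 = 6375 patients.

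**3. Highest share reachable and share at the required size.**

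| Ratio | Ceiling, every control matched | Share at the required size |
|---|---|---|
| 1:1 | 3200/8500 = 37.6% | 5400/2 = 2700; 2700/8500 = 31.8% |
| 2:1 | 6400/8500 = 75.3% | 6069 × 2/3 = 4046; 4046/8500 = 47.6% |

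A caliper can only lower these shares. If 2:1 meant two controls per rt-PA patient, the ceiling would be 1600/8500 = 18.8%.

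**4. How far the counts must move for 1:1 to pass.**
- Rounding alone (assuming 8500 to the nearest 500 and 3200 to the nearest 100): at most 3249/8250 = 39.4%.
- Equal proportional losses in both cohorts: still 37.6%.
- 10% of rt-PA patients lost: 3200/7650 = 41.8%. 20% lost: 3200/6800 = 47.1%.
- 10% of controls lost: 2880/8500 = 33.9%.
- Break-even with no control lost: T = 2 × 3200 = 6400, a loss of 1 − 6400/8500 = 24.7%. With 10% of controls lost: T = 2 × 2880 = 5760, a loss of 32.2%.

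With each count moved separately by up to 20% (an assumed range), the ceiling runs from 2560/10200 = 25.1% to 3840/6800 = 56.5%. On a grid of 10% steps, it exceeds 50% only where the rt-PA count falls and the non-reperfusion count rises.

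**5. The other reading of the rule.** Suppose that a patient can be matched if at least one control lies within the caliper. The ceiling is then 100%. A simulation shows how such a rule behaves (assumed: one normal covariate, equal variances, 8500 against 3200, caliper 0.2 SD of the logit). About 99.5% of rt-PA patients have a partner when the groups differ by 1 SD, and about 94% when they differ by 2 SD.

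**The case against.** The strongest reply is that the rule does not have to mean distinct pairs. Its wording comes before the sentence on selecting matched samples, so it could be an availability check, and then the ceiling does not bind. The support for distinct pairs is indirect. The required sizes come from power calculations and are silent on reuse. The conditional model ("the Chi-square test and conditional logistic regression model will be conducted") appears only in the SAP and only for the binary secondary outcomes; Protocol 9.G.i plans ordinary logistic regression. This stands as far as it goes: the reading is natural for a matched sample counted in patients, but it is not stated. It does not rescue the rule. On the availability reading it would almost never fire (step 5), so it would still say little about whether the cohorts differ.

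A second reply is that both documents tie feasibility to available sample size as well as to descriptive results, and that a 1:1 match discarding at least 62.4% of treated patients (1 − 0.376) may be a fair reason to think again. That is reasonable as policy. But the text defines the rule as a test of differing characteristics, and if it is a size check it conflicts with the plan's own required sizes, which fall below it at both ratios.

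A third reply is that the counts are approximate and may precede exclusions. They are also defined unequally: the 3200 carries the 4.5-hour limit and the 8500 does not. Excluding late rt-PA, missing treatment times and endovascular cases could reduce the rt-PA count, while the contraindication exclusion could reduce the controls. The loss needed is large, however, and SAP 7.1 treats the total as the number to be analysed.

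A reader might infer that matching is infeasible, or that the study must stop. The documents do not support that: 2:1 can pass, and the stated consequence is re-evaluation.

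**Conclusion.** The point holds as a defect in a decision rule. On the stated counts and with distinct pairs, the rule fires at 1:1 whatever the overlap, because the ceiling is 37.6% against a threshold of 50%. It also fires when the required sample is just reached at either ratio (31.8% at 1:1, 47.6% at 2:1). At 2:1 it can be met, but only with 306 patients more than the stated requirement (6375 − 6069).

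This rests on three things: no reuse of controls, 2:1 read as two rt-PA patients per control, and counts close to 8500 and 3200. At 1:1 the conclusion reverses only if the rt-PA cohort falls to 6400 or fewer with no control lost, or if the non-reperfusion count proves larger than stated.

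It would be tempting to conclude that the mortality comparison is biased or its error rate affected. The documents do not support that. The rule acts before analysis and changes no estimate or test, and residual imbalance is handled separately through standardised differences and adjustment. The arithmetic is certain; the distinct-pair reading is probable. It should be fixed before matching is run.

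**What to change.** In the protocol abstract, Protocol 9.G.i and SAP 11.1:

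- Express the rule as the share of the smaller (non-reperfusion) cohort matched within the 0.2 SD caliper, with a threshold tied to the required size for the chosen ratio: 2700/3200 = 84% at 1:1 (5400 patients) or 6069/3 = 2023 and 2023/3200 = 63% at 2:1 (6069 patients). Recompute both on the final cohort counts.
- State whether controls may be reused (also in SAP 10.1, where the software is named) and which cohort the 2 in 2:1 refers to.
- Fix the ratio before outcomes are examined.
- Judge similarity of characteristics by the standardised differences that SAP 11.1 already plans before and after matching, and keep the adjustment for residual imbalance.

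Do not replace the rule with a requirement that each rt-PA patient has at least one control within the caliper. With about 3200 controls that would almost never fire, as the simulation shows.

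The cost is a few sentences in four places and a recalculation of two percentages. No new data are needed.
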